2.0 Objectives

2.1 Overall Study Objectives:

The overarching goal of this study is to pilot a randomized controlled trial (RCT) of the Pediatric Cancer Resource Equity (PediCARE) intervention to determine feasibility of intervention administration in a childhood cancer population. Secondary goals include generation of effect size estimates for a primary endpoint of reduction in household material hardship (HMH) and a secondary endpoint of Emergency Department and Intensive Care Unit utilization to support

planning of a subsequent definitive multi-center RCT. PediCARE is a poverty-targeted intervention utilizing direct resource provision of groceries and transportation.

2.2 Specific Aims:

Pilot RCT to determine feasibility

To conduct a pilot RCT of the PediCARE intervention in 40 newly diagnosed pediatric cancer families with HMH at DFCI and UAB. Families in the intervention arm will receive PediCARE for 6-months. The control group will receive usual care. Data will be collected by parent survey at baseline and 6-months. The primary outcome will be defined as feasibility. Secondary outcomes will include improvement in HMH scores (range 0-4) at 6-months compared to baseline and Emergency Department (ED) and Intensive Care Unit (ICU) admissions. Analyses will focus on effect size estimates to plan a subsequent RCT.

H2a. Feasibility will be demonstrated by recruitment rate of 75% and follow-up survey data collection of 80% per arm.

H2b: There will be a trend towards a reduction in HMH scores (primary endpoint) and lower proportion of patients experiencing an ED visit or ICU admission over 6-months in the PediCARE versus usual care group.

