8.0 Study Endpoints

8.1 Feasibility: The primary endpoint of this study is feasibility. Feasibility will be defined as at least 75% consent to randomization and at most 20% attrition per arm. We will assess process barriers to feasibility including recruitment, attrition by arm and parent report of PediCARE component utilization (i.e. food and transportation).

[figure not shown]
Study Timeline (Months)	Months 1 -6 Year 1	Months 7- 12 Year 1	Months 1-6 Year 2
Screen and enroll families (6 months)			
Intervention administration (6 months)			
Data analysis			

8.2 HMM and Utilization: The secondary endpoints of this study will be used to generate effect size estimates to support planning of a subsequent RCT. Secondary endpoints will be evaluated comparing recipients of PediCARE versus Usual Care. Secondary outcomes include change in HMM utilizing an HMM score (range 0-4) at 6-months compared to baseline; and proportion of patients experiencing an Emergency Department (ED) visit or Intensive Care Unit (ICU) admission over 6-months.

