11.0 Statistical Considerations

Accrual: Annually, 420 new patients receive chemotherapy at DFCI and 120 at UAB. Based on prior institutional HMH data, we estimate 20% will be eligible to participate at DFCI (N=84) and 30% will be eligible to participate at UAB (N=36). We estimate a 75% consent rate for a total possible annual sample size of N=90 patients (63 DFCI, 27 UAB). Forty patients will be accrued over 6-months at DFCI (n=28) and UAB (n=12). Patients will be randomized 1:1 by site to PediCARE versus UC.

Analysis Plan: Sample demographic, disease, treatment and utilization variables from the survey instruments and medical chart will be described by summary statistics.

The rate of consent to randomized intervention and the 6-month completion will be estimated along with a 90% confidence interval (CI). Feasibility will be established if the upper bound of the CI contains 75% and 80% for consent and follow-up respectively. With an estimated 60 eligible patients at 6 months, at least 39 (65%; 90% CI 53.6-75.2%) need to enroll for the upper bound of the 90% CI contain 75%. With an estimated 40 randomized patients, at least 28 (70%; 90% CI 56.0-81.7%) need to have complete 6-month data to have the upper bound of the 90% CI contain 80%. The 6-month completion rate will also be estimated along with a 90% CI by randomized arm (PediCARE and UC).

For each family, the difference between 6-month and baseline HMH scores will be categorized as improved (change score <0) or not improved (change score ≥0). For each arm, the proportion of families with improved HMH at the completion of the intervention (6-months) will be estimated along with a 90% exact CI. Based on prior data, we assume a 30% resolution in HMH in UC, thus the 90% CI will be within ±24.9%. For each arm, the per patient number of ED visits and ICU stays will be summarized (median, range). The proportion of patients with at least one ED and/or ICU visit will be estimated for each arm, as well as the difference between arms, along with a 90% confidence interval. Additionally, the rate of HMH at the completion of the intervention pilot (6-months) along with a 90% exact confidence will be estimated for UC and PediCARE. For the PediCARE arm, the cost per patient, study team contact hours, and proportion with successful receipt of all intervention components will be described overall and by site.

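### Section 11.0 reduces change in the 0-4 HMH score to improved or not improved, so the planned outputs do not separate unchanged from worsened families and give no mean change or SD (low priority, secondary endpoint).

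*Combined protocol and SAP*

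**What the plan says.** Section 8.2 names as a secondary outcome "change in HMM utilizing an HMM score (range 0-4) at 6-months compared to baseline" (HMM there is evidently HMH). It adds that the secondary endpoints "will be used to generate effect size estimates to support planning of a subsequent RCT", and that "Secondary endpoints will be evaluated comparing recipients of PediCARE versus Usual Care".

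Section 2.1 sets as a secondary goal the "generation of effect size estimates for a primary endpoint of reduction in household material hardship (HMH"). Section 2.2 words the outcome as improvement in the 0-4 score at 6 months, and its hypothesis H2b reads "There will be a trend towards a reduction in HMH scores (primary endpoint").

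Section 11.0 plans two HMH outputs. First, each family's change is "categorized as improved (change score <0) or not improved (change score ≥0"), and the proportion improved is estimated in each arm with a 90% exact CI. Second, the rate of HMH at 6 months is estimated in each arm, also with a 90% exact CI. The general descriptive sentence covers demographic, disease, treatment and utilization variables and does not name the HMH score.

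For ED and ICU use the same section says "the per patient number of ED visits and ICU stays will be summarized (median, range"). It also gives the proportion with at least one visit in each arm, "as well as the difference between arms, along with a 90% confidence interval".

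**The concern.** The not-improved category holds every change of zero or more, so a family going from 1 to 4 is reported like one staying at 1. If HMH at 6 months means a score of at least 1, the 6-month rate does not separate them either, because both still have HMH.

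Two things are then missing for planning the next trial. A trial whose endpoint is the score itself needs a mean change and an SD, and no planned output supplies them. And if groceries and transport help partly by stopping families from getting worse, that part of the effect does not appear. The protocol treats worsening as a distinct possibility: Section 13.0, item 5, lists persistent and worsened HMH as separate outcomes under usual care (UC).

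**Working it through.** **Inputs from the documents.** 40 families randomized 1:1, so 20 per arm (Section 4.0). Attrition of at most 20% per arm (Section 8.1), so 20 × 0.80 = 16 per arm with data. Assumed 30% resolution of HMH in UC (Section 11.0). HMH for eligibility means at least one of four needs (Section 3.1). The same threshold is assumed here for the 6-month rate.

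**Step 1: the plan's own figures.** Clopper-Pearson 90% intervals reproduce the two feasibility intervals: 39/60 gives 53.6-75.2% and 28/40 gives 56.0-81.7%. For the HMH proportion at 30%, 6/20 gives 14.0-50.8%, a largest distance of 20.8 points. For 5/16 the interval is 13.2-54.8%, a largest distance of 23.6 points. The stated bound of ±24.9% is not reproduced exactly, but it is true as an upper bound at both sample sizes and has no bearing on this point.

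**Step 2: what the two planned outputs determine.** Take families with baseline of at least 1.
- Score 0 at 6 months: improved, no HMH.
- Lower than baseline but at least 1: improved, HMH present.
- Same as baseline: not improved, HMH present.
- Higher than baseline: not improved, HMH present.

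The last two are indistinguishable. A family that screened positive with a site provider but scored 0 on the baseline survey would be an exception, since any HMH at 6 months would then be a worsening.

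**Step 3: an illustration (counts assumed, not forecast).** 20 per arm, all baselines at least 1, and the six improved families in each arm reach 0.

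| | Improved | Unchanged | Worsened |
|---|---|---|---|
| PediCARE | 6 | 12 | 2 |
| UC | 6 | 6 | 8 |

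Planned outputs in both arms: 6/20 = 30% improved (14.0-50.8%) and 14/20 = 70% HMH rate (49.2-86.0%).

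Not planned: worsened 2/20 = 10% (1.8-28.3%) and 8/20 = 40% (21.7-60.6%). The difference is -30 points (Newcombe 90% CI -49.3 to -7.4).

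If all baselines are 1 and each move is one domain, mean change is (-6 + 2)/20 = -0.20 (SD 0.62) and (-6 + 8)/20 = +0.10 (SD 0.85). The difference is -0.30 (Welch 90% CI -0.70 to +0.10).

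**Step 4: logical bounds on mean change.** With common baseline b, n families, k improved and all k reaching 0:
- lower bound = -b·k/n (nobody worsens);
- upper bound = (-b·k + (4 - b)(n - k))/n (all the rest go to 4).

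| Baseline b | n = 20, k = 6 | n = 16, k = 5 |
|---|---|---|
| 1 | -0.3 to +1.8 | -0.31 to +1.75 |
| 2 | -0.6 to +0.8 | -0.63 to +0.75 |
| 3 | -0.9 to -0.2 | -0.94 to -0.25 |

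For b = 1 or 2 the planned outputs do not fix even the sign of the mean change. For b = 3 they do.

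**Step 5: would three-category counts be enough?** No. With 6 improved, 10 unchanged, 4 worsened and mixed baselines, mean change can lie anywhere from (-4×6 + 1×4)/20 = -1.0 to (-1×6 + 3×4)/20 = +0.3. A score summary is needed too.

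**Step 6: precision of the additions.** Newcombe 90% half-width for the between-arm difference: ±20.8 points for 4/20 v 4/20 worsened, ±22.9 points for 6/20 v 6/20 improved. For the difference in mean change, t(0.95, 2n - 2) × SD × √(2/n):

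| Assumed SD | n = 20 per arm | n = 16 per arm |
|---|---|---|
| 0.75 | ±0.40 | ±0.45 |
| 1.0 | ±0.53 | ±0.60 |
| 1.5 | ±0.80 | ±0.90 |

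The documents give no SD for the change.

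**The case against.** The strongest case on the other side is that the proportion improved is a direct, prespecified measure of what Section 2.2 calls the outcome. Section 11.0 attaches a precision statement to a 30% rate, so the choice was considered. That stands: the dichotomy is an analysis choice that loses information and does not contradict the aims. Section 8.2's change in score and H2b's reduction in scores are wider than it, however.

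A reader might infer that HMH gets no other summary, or that the arms cannot be compared on it. The documents do not support either. The 6-month rate is a dichotomized summary of the 6-month score. With baselines of at least 1, the two outputs together identify resolved, improved but unresolved, and not improved. The difference in proportion improved, with a CI, can be computed from the two planned counts, so a binary endpoint could be sized from them.

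A reader might also infer that worsening is known to be common in the enrolled population. Section 1.0's 20% at diagnosis and 30% after six months covers all families. The rise could come entirely from families without HMH at diagnosis, who are not eligible here. It makes worsening plausible and gives no rate for it.

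The illustration is built to hold improvement equal and assumes complete data. With 16 per arm, 2/16 v 6/16 worsened gives -25 points (Newcombe 90% CI -46.9 to +0.4), which includes zero. Finally, both surveys collect the domain items, so the summaries could be added at reporting. What is lost is their prespecification, in a trial where Section 9.2 says the study team knows the assignments.

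**Conclusion.** The point holds as a low-priority reporting improvement to a secondary, estimation-only endpoint. The planned outputs yield a binary effect size. They do not separate unchanged from worsened families with baseline scores of at least 1, and they provide no mean, median, spread or distribution of the score or its change. A benefit through preventing worsening would not be visible, and a score-based later trial would lack a mean change and SD.

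How much this would matter in practice cannot be estimated from the documents. The 10% v 40% example and the bounds on mean change rest on assumed counts and baselines and show only what the outputs leave open. The conclusion also assumes that HMH at 6 months means at least one need, as for eligibility. The feasibility decision does not depend on any of this.

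**What to change.** In Section 11.0, keep the proportion improved and add two sentences, using the same scores:

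1. For each arm, report the numbers improved (<0), unchanged (0) and worsened (>0), with a 90% exact CI for the proportion worsened, and the mean (SD) or median (range) of the baseline score, 6-month score and change.
2. Report descriptive PediCARE minus UC differences with 90% CIs for mean change and proportion worsened, and state the difference in proportion improved explicitly, as is already done for the ED/ICU proportion.

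No tests are needed. The cost is a few more table rows, with no new data, staff or patients. The downside is the wide intervals shown in the working, which should be presented as descriptive.

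### The plan promises a PediCARE-versus-usual-care effect size for household material hardship, but Section 11.0 estimates HMH only within each arm, as yes/no proportions

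*Combined protocol and SAP*

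**What the plan says.** Section 2.1 lists effect size estimates for reduction in HMH among the pilot's secondary goals, in support of a definitive multi-center trial. Section 2.2 adds: "Analyses will focus on effect size estimates to plan a subsequent RCT". Hypothesis H2b is framed on HMH scores, PediCARE against usual care (UC), and labels HMH its primary endpoint, ahead of ED/ICU use.

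Section 8.2 states: "Secondary endpoints will be evaluated comparing recipients of PediCARE versus Usual Care". It gives the scale as follows (the section prints HMM for HMH): "Secondary outcomes include change in HMM utilizing an HMM score (range 0-4) at 6-months compared to baseline".

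Section 11.0 first reduces each family's change score to improved (below 0) or not improved (0 or above). Then: "For each arm, the proportion of families with improved HMH at the completion of the intervention (6-months) will be estimated", with an exact 90% CI. It assumes 30% resolution in UC and gives a precision of ±24.9%. It also plans the 6-month HMH rate in each arm with an exact 90% CI. For the proportion of patients with an ED and/or ICU visit, the same paragraph says the quantity "will be estimated for each arm, as well as the difference between arms, along with a 90% confidence interval".

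**The concern.** A proportion improved within one arm is not a treatment effect. Families enter because they screened positive for HMH (Section 3.1), so some will improve in either arm through regression to the mean and usual support; the plan itself expects 30% resolution in UC. Only the contrast between randomized arms removes this, and Section 11.0 plans that contrast for ED/ICU use but not for HMH.

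The cut at zero also discards information. A fall from 4 to 1 counts the same as a fall from 2 to 1, and a worsening counts the same as no change.

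At stake is the pilot's planning output. A later trial powered on HMH needs a between-arm difference with its uncertainty and, if it uses the 0-4 score, an SD. Neither is specified.

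**Working it through.** **1. What is promised and what is planned**

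| Item | Sections 2.0 and 8.2 | Section 11.0 |
|---|---|---|
| HMH scale | 0-4 score, change from baseline | Improved / not improved; HMH present / absent at 6 months |
| HMH comparison | PediCARE versus UC | None; each arm separately |
| HMH score mean, SD, adjusted difference | Needed for an effect size on the score | None |
| ED/ICU comparison | PediCARE versus UC | Difference between arms, 90% CI |

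No other section supplies the HMH contrast.

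**2. The plan's own figures**

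Inputs: 20 per arm (14 + 6, Section 4.0); 30% in UC and 90% confidence (Section 11.0); up to 20% attrition per arm (Section 8.1), so 0.8 × 20 = 16 completers.

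The feasibility intervals reproduce as exact (Clopper-Pearson) 90% CIs: 39/60 gives 53.6-75.2% and 28/40 gives 56.0-81.7%.

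The ±24.9% does not reproduce in the same way:

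- Exact 90% CI for 6/20: 14.0-50.8%, that is -16.0/+20.8 points.
- Exact 90% CI at 30% with n = 16: -17.7/+23.6 points.
- Single-arm 90% Wald, 1.645 × sqrt(0.30 × 0.70/n): ±16.9 points (n = 20), ±18.8 points (n = 16).

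It does reproduce as a half-width for a difference between two arms of 20 with UC at 30%. That half-width is largest when the other arm is at 50%:

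1.645 × sqrt(0.30 × 0.70/20 + 0.50 × 0.50/20) = 1.645 × sqrt(0.0230) = 0.249.

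A single-arm 95% Wald interval with n = 13 also gives 24.9, but neither that n nor that level appears in the plan.

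**3. Precision of the missing estimate**

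The documents give no PediCARE rate, so 30-70% is assumed, with UC at 30%:

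- 20 per arm: 90% Wald half-width 23.8 to 24.9 points.
- 16 per arm: 26.7 to 27.9 points.
- Newcombe 90% CI for 50% versus 30%: difference 20 points, -5.2 to 42.0 (20 per arm) or -8.0 to 44.1 (16 per arm).

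For the score, the SD of change is not given. With an assumed SD of 0.75-1.25, the 90% half-width t × SD × sqrt(2/n) is 0.40 to 0.67 score points (n = 20, t = 1.686) or 0.45 to 0.75 (n = 16, t = 1.697).

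**4. Two arm-level CIs are not the CI of the difference**

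Take 6/20 against 11/20. The exact 90% CIs are 14.0-50.8% and 34.7-74.1%, overlapping by 50.8 - 34.7 = 16.1 points. The difference is 55 - 30 = 25 points:

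- Wald: 25 ± 1.645 × sqrt(0.21/20 + 0.2475/20) = 25 ± 24.9, or 0.1 to 49.9 points.
- Newcombe, from Wilson limits 16.4-48.4% and 37.2-71.6%: lower 25 - sqrt(17.8² + 18.4²) = -0.6; upper 25 + sqrt(16.6² + 13.6²) = 46.5 points.

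The arm-level intervals show neither result, and the choice of method moves the lower limit across zero. The method should therefore be named in advance.

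**5. Cost of dichotomizing (illustrative only)**

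A simulation with 20 per arm assumed four domains, persistence 0.7-0.8, onset 0.1-0.2, and an intervention cutting food and transport hardship by 35-50%. The improved/not-improved comparison had about 70-90% of the efficiency of a baseline-adjusted comparison of the 0-4 score; a repeat gave 68-82%. At 70%, 20 families per arm do the work of 0.7 × 20 = 14. None of these inputs comes from the documents.

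**The case against.** The trial is a 40-family pilot whose primary endpoint is feasibility. H2b looks only for a trend, and no decision rule depends on HMH. Both arm proportions will be reported, so anyone can subtract them and compute a CI, and Section 8.2 already commits to comparing the arms. The ±24.9% suggests a dropped phrase, not a design without a contrast. The binary endpoint is prespecified with a clear cut, and the next trial might use a responder endpoint. Adjusted analysis of a five-level score is one option among several. Regression to the mean cancels between randomized arms.

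Much of this limits the seriousness of the point without removing it. A crude difference can be recovered afterwards, but its CI method is not fixed, and the score SD cannot be recovered from two proportions. Sections 2.2 and 8.2 name the 0-4 score as the HMH outcome, so summarizing it is part of what was promised. Regression to the mean does cancel in the contrast, which is the reason to plan one. The criticism of the 6/20 versus 11/20 example stands: it shows only that two intervals are not the interval of their difference, and says nothing about significance. The simulation is illustrative and the conclusion does not need it.

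**Conclusion.** The concern holds. Followed as written, Section 11.0 would not report the HMH effect size that Sections 2.0 and 8.2 set out to obtain, nor any mean or SD of the 0-4 score. This rests on the text alone.

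That a between-arm difference was intended is an inference from the numerical match: 24.9 points for a two-arm difference, against -16.0/+20.8 for the per-arm exact interval to which the figure is attached. On that reading the stated precision assumes no attrition; at the tolerated 20% the half-width rises to as much as 27.9 points. The estimate will be imprecise either way, so its interval should be planned and reported.

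This should be corrected, but it does not threaten the primary feasibility objective.

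**What to change.** Amend Section 11.0 before the 6-month data are analysed:

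1. Add the PediCARE-minus-UC difference in proportion improved, with a 90% CI and a named method (for example Newcombe).
2. Add the between-arm difference in 6-month HMH score (0-4), adjusted for baseline score and site (the stratification factor), with its 90% CI and residual SD. Name it as the effect size estimate for the next trial.
3. Report the mean and SD of the change score by arm. Keep the per-arm proportion improved and 6-month HMH rate as descriptive summaries.
4. Relabel ±24.9% as the half-width of a between-arm difference, or recompute it for the per-arm interval, and give the value allowing for 20% attrition.
5. State whether the assumed 30% refers to resolution or to improvement. A fall from 4 to 3 is improvement without resolution.

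The cost is a few lines of text and one regression. The baseline and follow-up surveys already collect the HMH items, so no family is asked for anything more.

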4.0 Planned Enrollment

This study aims to enroll a total of 40 participants as follows:

Pilot RCT DFCI and UAB: The target sample size is 40 participants. At DFCI, a total of 28 participants will be enrolled and randomized (thus 14 participants will receive PediCARE and 14 participants will receive UC). At UAB a total of 12 participants will be enrolled and randomized (thus 6 participants will receive PediCARE and 6 participants will receive UC).

Families will be recruited consecutively at each site over a 6-month time period. Patients will be randomized 1:1 to PediCARE versus Usual Care (UC) and randomization will be stratified by site.

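### The ±24.9% precision quoted for HMH in Section 11 is not that of the per-arm exact 90% interval it follows; it matches a between-arm difference that the section does not plan for HMH

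*Combined protocol and SAP*

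**What the plan says.** The analysis plan in Section 11.0 classifies each family's change in HMH score as "improved (change score <0) or not improved (change score ≥0". For each arm, the proportion "with improved HMH at the completion of the intervention (6-months) will be estimated along with a 90% exact CI". The next sentence gives the planned precision: "Based on prior data, we assume a 30% resolution in HMH in UC, thus the 90% CI will be within ±24.9" per cent. It names no sample size, no formula and no contrast between arms.

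Further on, Section 11.0 also plans "the rate of HMH at the completion of the intervention pilot (6-months) along with a 90% exact confidence" interval in each arm. It specifies a between-arm difference with a 90% interval for ED/ICU use, but not for HMH.

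Two other sections bear on the reading. Section 4.0 says "The target sample size is 40 participants", made up of 14 per arm at DFCI and 6 per arm at UAB, so 20 per arm. Section 8.0 sets "at most 20% attrition per arm" and says of the HMH and utilisation outcomes: "Secondary endpoints will be evaluated comparing recipients of PediCARE versus Usual Care".

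**The concern.** The sentence presents the figure as a consequence of 30% in usual care, straight after naming a per-arm exact interval. A reader will take it as that interval's precision, but it does not reproduce at 20 per arm.

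The secondary outcomes exist to supply effect-size estimates for the next trial, and this is the only planned-precision figure for HMH. Whoever plans that trial cannot tell which quantity, sample size or method it describes. The 30% is also ambiguous. It is called resolution, while the outcome beside it is improvement, and a family that moves from a score of 3 to 2 has improved without resolving.

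**Working it through.** **Inputs.** 90% confidence, exact method, usual-care rate 30% (Section 11.0); 20 per arm (Section 4.0: 14 + 6); at most 20% attrition per arm (Section 8.1), so 20 × 0.8 = 16 completers.

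**Step 1: confirm the method on the plan's own intervals.** The exact (Clopper-Pearson) 90% limits for x of n are the 5th percentile of Beta(x, n − x + 1) and the 95th percentile of Beta(x + 1, n − x).

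- 39/60: 53.64% to 75.21%. The plan prints 53.6 to 75.2.
- 28/40: 55.97% to 81.69%. The plan prints 56.0 to 81.7.

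Both feasibility intervals reproduce, so the choice of exact method does not explain the mismatch below.

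**Step 2: the per-arm interval for HMH.**

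| Count | Estimate | Exact 90% CI | Distance below / above | Half-width |
|---|---|---|---|---|
| 6/20 | 30.0% | 13.96–50.78% | 16.0 / 20.8 | 18.4 |
| 5/16 | 31.25% | 13.21–54.83% | 18.0 / 23.6 | 20.8 |

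The count 5/16 is the nearest whole number to 30% of 16 (4.8). Over all possible counts, the largest distance from estimate to limit is 20.8 points at n = 20 and 23.6 at n = 16. Neither gives 24.9.

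**Step 3: other one-arm methods at 30%, n = 20.**

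- 90% normal approximation: 1.645 × √(0.3 × 0.7 / 20) = 16.85.
- The same with continuity correction: 16.85 + 100/40 = 19.35.
- 95% exact: 18.1 below, 24.3 above.
- 95% normal approximation: 20.1.

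None gives 24.9.

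**Step 4: a between-arm difference.** The 90% normal-approximation half-width with usual care at 30% and PediCARE at p is 1.645 × √[(0.3 × 0.7 + p(1 − p)) / n].

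| p | Half-width, n = 20 per arm |
|---|---|
| 30% or 70% | 23.84 |
| 40% or 60% | 24.67 |
| 45% or 55% | 24.88 |
| 50% | 24.945 |

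The maximum is at p = 50%, where p(1 − p) peaks: 1.645 × √(0.46/20) = 24.945, printed as 24.9. No PediCARE rate has to be assumed, because this value bounds all of them. That fits a sentence that gives only the usual-care rate and says the interval lies within a limit.

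At 16 completers per arm the same maximum is 1.645 × √(0.46/16) = 27.89.

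**Step 5: improved or resolved.** Section 3.1 requires every family to screen positive for HMH. Resolution therefore corresponds to the complement of the separately planned 6-month HMH rate. The exact interval is symmetric under this exchange: 30% resolved (6/20) mirrors 70% with HMH (14/20), with limits 100 − 50.78 = 49.2% and 100 − 13.96 = 86.0%. The width at 30% is therefore the same for either outcome. What stays unknown is which outcome the 30% belongs to.

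**The case against.** The strongest defence is that the sentence states a bound, and as a bound it is true. At 20 per arm no exact limit lies more than 20.8 points from its estimate, and at 16 none lies more than 23.6. This stands: at the planned size and at the attrition limit the sentence is loose, not false.

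A second defence is that the figure does follow from 30%, 90% confidence and 20 per arm if a between-arm difference was meant, and Section 8.2 does call for comparing the arms. This also stands as the likelier explanation. It does not rescue the sentence, because Section 11.0 mentions neither an HMH difference nor a normal approximation for HMH. The defect then lies in the label and the missing estimate.

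A reader might go further and infer that the bound breaks at the minimum accepted follow-up. Section 11.0 says "at least 28 (70%; 90% CI 56.0-81.7%) need to have complete 6-month data to have the upper bound of the 90% CI contain 80" per cent, and an even split would leave 14 per arm, where 4/14 gives 10.4% to 54.0%, 25.4 points above the estimate. The documents do not carry that inference:

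- 28 of 40 is a pooled feasibility threshold, not a precision assumption, and the even split is not stated.
- 14 of 20 means 30% attrition in each arm, beyond the 20% in Section 8.1.
- The excess is about half a point (25.4 − 24.9), and only if ± means the longer side of an asymmetric interval. As a half-width, 4/14 gives 21.8, and the largest value over all counts at n = 14 is 23.6.

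**Conclusion.** The point holds as one of labelling and reproducibility. The ±24.9% is not the precision of the per-arm exact interval it follows: at 6/20 the half-width is 18.4 and the longer side 20.8. The conclusion rests on 20 per arm, the stated 30% and the exact method, which the plan's other two intervals confirm.

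The between-arm origin is an inference from agreement to one decimal and should not be reported as what the authors did. If it is right, two further gaps follow. Section 11.0 lists no HMH difference although Section 8.2 compares the arms, and the figure allows for no attrition (±24.9 becomes about ±27.9 at 16 per arm).

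A reader might also infer that the sample size or the feasibility conclusion is unsound. The documents do not support this. The figure is a planning statement for a secondary endpoint, the feasibility rule uses separate intervals that reproduce, and the final HMH intervals will come from the observed data. The effect is minor.

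**What to change.** Replace the sentence in Section 11.0 with the per-arm precision, for example:

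> With about 30% of usual-care families improved, the exact 90% CI is about 14% to 51% with 20 families (6/20) and about 13% to 55% with 16 completers (5/16).

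State whether the 30% is the proportion improved (a fall in score) or the proportion whose HMH resolved. If it is resolution, attach the sentence to the 6-month HMH rate.

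The trial statistician should confirm which quantity ±24.9% was meant to describe. If it was the between-arm difference, keep it under that label, add the HMH difference with its 90% CI and method to Section 11.0 as is already done for ED/ICU use, and give the value at the attrition limit (about ±27.9 with 16 per arm).

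The cost is one sentence, or two if the difference is added. Conduct, sample size and data collection do not change.
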